## **5.11 SIGNAL MANAGEMENT AND RISK MANAGEMENT**

Genentech is responsible for safety signal management (signal detection and/or evaluation) for their own Product. However, it is agreed that TriCore, as Sponsor of the study, will be primarily responsible for assessment of the benefit-risk balance of the study.

If TriCore issues a safety communication relevant for Genentech (i.e., a safety issue that notably impacts the benefit-risk balance of the study and / or triggers any changes to the study) this will be sent to Genentech within five (5) business days of its internal approval.

As needed, Genentech will reasonably assist TriCore with signal and risk management activities related to the Product within the study.

Genentech will also provide TriCore with any new relevant information that may modify, or supplement known data regarding the Product (e.g., relevant Dear Investigator Letter).

## **5.12 COMPLIANCE WITH PHARMACOVIGILANCE AGREEMENT / AUDIT**

The Parties shall follow their own procedures for adherence to AE reporting timelines.

Each Party shall monitor and, as applicable, request feedback from the other Party regarding AE report timeliness in accordance with its own procedures. The Parties agree to provide written responses in a timely manner to inquiries from the other Party regarding AE reports received outside the agreed upon Agreement timelines. If there is any detection of trends of increasing or persistent non-compliance to transmission timelines stipulated in this Agreement, both Parties agree to conduct an ad hoc or institute a regular joint meeting to address the issue.

In case of concerns related to non-compliance of processes, other than exchange timelines, with this Agreement, the Parties will jointly discuss and collaborate on clarifying and resolving the issues causing non-compliance. Every effort will be made by the non-compliant Party to solve the non-compliance issues and inform the other Party of the corrective and preventative actions taken.

Upon justified request, given sufficient notice of no less than sixty (60) calendar days, an audit under the provisions of this Agreement can be requested by either Party. The Parties will then discuss and agree in good faith upon the audit scope, agenda, and execution of the audit. The requesting Party will bear the cost of the audit.

## **6. STATISTICAL CONSIDERATIONS**

### **6.1 DETERMINATION OF SAMPLE SIZE**

The algorithms that we use to determine the community of interest is based on meeting the hot-spot or testing desert criteria and a weighted value of the social vulnerability index (SVI) which defined from 0-1.0 and is determined at the census tract level. This includes factors such as socioeconomic status, household composition, race/ethnicity, housing and transportation access. Each census tract is composed of 2500-4000 individuals and we anticipate enrolling 200-250 patients at each deployment resulting in approximately 5-10% of the census tract tested at each deployment. The 20 community centers that we will partner with have an average SVI pf 0.85 (0.55-1.0). There are

approximately 140 census tracts in the Albuquerque Metropolitan Area that will be tracked during this study. These high vulnerability locations are aggregated in six zip codes with the following demographic composition of race and ethnicity.

While test positivity rate will change based on the current epidemiology, we expect 10-20% positivity for Influenza during the treatment study period as we anticipate beginning the study period during respiratory virus season with increased viral positivity. Based on this, we expect 20-50 patients will be eligible for influenza treatment at each deployment with an additional 20-50 patients positive for COVID-19 who will receive referrals for COVID-19 treatment at other treatment locations. We expect that we will be able to provide treatment to approximately 430 individuals based on the assumption that 90% will be in the treatment window and 80% will test positive.

The mobile testing unit will be deployed a minimum of 2 times per week following the determination of the influenza season by the New Mexico Department of Health. We expect to screen 50-100 patients per week for the duration of the influenza season (approximately 12 weeks) for a total of 600-1,2000 patients. With an anticipated 20-10% positivity rate for influenza, we expect at least 5-10 patients per week to be eligible for treatment for a total of 60-120 patients eligible over the course of the study. All subjects will be provided a survey to evaluated their ability to access respiratory virus testing and their acceptance of and trust in using a mobile unit for access to treatment and therapeutics. As per the New Mexico Test to Treat protocol, all patients will receive a follow-up phone call 24-48 hours following treatment. Additionally, all patients enrolled in the study will receive a follow-up phone call 14-days following the initial screening visit.

	Enrollment per deployment	Number of Deployments	Total Enrolled	Positivity Rate (Influenza)	Within Treatment Window	Expected Treated (total study)
Influenza Test to Treat	50-100	12	600-1200	10-20% (60-240)	90%	54-180

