## **4. MATERIALS AND METHODS**

### **4.1 PATIENTS**

Approximately 600-1,200 patients will be enrolled in the study to be screened for influenza A&B and SARS-CoV2. We expect approximately 10% positivity rate for 60-120 patients to be eligible for treatment.

There are approximately 140 census tracts in the Albuquerque Metropolitan Area that will be tracked during this study.

Zip Code	Race/Ethnicity (% population)							
	Hispanic	Non-Hispanic/White	Black	Native Indian	Asian	Hawaiian	Other	2 or More
87108	51.5	33.7	3.7	4.7	1.4	0.0	0.2	2.6
87123	44.3	40.7	3.5	3.5	4.6	0	0.1	3.7
87121	82.5	9.7	2.3	3.8	0.4	0.2	0.1	1
87102	61.4	26.6	3.1	5.6	10.7	0	0.31	1.5
87105	79.6	14.1	0.6	4.4	0.3	0.1	0.1	0.6
87106	38.1	48.2	3.3	3.1	3.9	0	0.5	2.9

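### Section 6.1 gives planning figures that cannot all be true: the table's own inputs yield 54–216 treated, not 54–180, and the text's 430 treated and 200–250 per deployment do not fit a 600–1,200 patient study

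*Combined protocol and SAP*

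**What the plan says.** Section 4.1 sets the size of the study: "Approximately 600-1,200 patients will be enrolled in the study". The table in Section 6.1 has the same total, built from 50–100 patients in a column headed "Enrollment per deployment" and 12 deployments. It then gives 10–20% positivity (60–240 patients), 90% within the treatment window, and 54–180 expected treated.

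The text just above the table describes the rate differently. It says "The mobile testing unit will be deployed a minimum of 2 times per week" and "We expect to screen 50-100 patients per week for the duration of the influenza season (approximately 12 weeks". Section 3.1 has the same weekly plan. Section 3.2 ends the study at the later of 12 weeks of deployment and the end of the influenza season, so 12 weeks is a minimum.

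The opening of Section 6.1 uses other figures again:

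- Enrolment and reach: "we anticipate enrolling 200-250 patients at each deployment resulting in approximately 5-10% of the census tract tested at each deployment", with tracts of 2,500–4,000 people.
- Positivity: "we expect 10-20% positivity for Influenza during the treatment study period".
- Eligible: "we expect 20-50 patients will be eligible for influenza treatment at each deployment".
- Treated over the study: "approximately 430 individuals based on the assumption that 90% will be in the treatment window and 80% will test positive".

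**The concern.** Section 6.1 is the only justification of study size, and it seems to describe more than one study. The upper end of the table's last column does not follow from the columns before it. The opening text assumes 80% positivity shortly after assuming 10–20%, and its enrolment per deployment is several times the table's. The table and the text disagree on the number of deployments and on whether 50–100 is a weekly or a per-deployment figure.

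Two stated quantities are at stake. The first is the number of patients the study expects to treat, who also form the safety population in Section 6.4; it can be read as a maximum of 180, a maximum of 216, or about 430. The second is the share of a tract reached at each deployment. The primary objective (Section 2.1) is an effect on the hot spot score of a census tract, so this share is what a reader would use to judge whether such an effect is plausible.

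**Working it through.** **1. The Section 6.1 table.** Inputs: 50–100 per deployment, 12 deployments, 10–20% positive, 90% in window.

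- Enrolled: 50 × 12 = 600; 100 × 12 = 1,200. Matches the table.
- Positive: 600 × 0.10 = 60; 1,200 × 0.20 = 240. Matches the table.
- Treated, lower end: 60 × 0.90 = 54. Matches the table.
- Treated, upper end: 240 × 0.90 = 216. The table prints 180.

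The printed 180 corresponds to 180 / 0.90 = 200 positives, not the 240 in the same row. It is 1 − 180/216 = 17% too low. An extra 80% factor does not explain it: 216 × 0.80 = 172.8, and the lower end would then be 43.2.

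**2. The figure of 430 treated.** The two factors stated beside it reproduce it from 600 patients: 600 × 0.90 × 0.80 = 432 (1,200 would give 864). Other products of the plan's figures also give 432:

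- 12 deployments × 50 eligible × 0.90 × 0.80
- 24 deployments × 100 × 0.20 × 0.90
- 24 deployments × 20 eligible × 0.90

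The plan does not say which was meant. Against the 600–1,200 plan, 430/216 = 2.0. With 90% in window, 430 treated would need positivity of 430/(0.90 × 1,200) = 40% to 430/(0.90 × 600) = 80%, against the stated 10–20%.

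**3. 200–250 per deployment.**

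- Over 12 deployments: 2,400–3,000 enrolled.
- Over 24 deployments: 4,800–6,000 enrolled.
- Eligible per deployment: 200 × 0.10 = 20; 250 × 0.20 = 50. This is the stated 20–50. It is a count of positives before the 90% factor.
- Tract coverage: 200/4,000 = 5%; 250/2,500 = 10%. This is the stated 5–10%.

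So the 20–50 eligible and the 5–10% coverage follow from 200–250 and do not survive without it.

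**4. Deployments and units.** 2 per week × 12 weeks = at least 24, against 12 in the table. There are two readings of 50–100:

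- Per week: 50–100 × 12 weeks = 600–1,200, which fits the stated total. With two deployments a week, each enrols 25–50.
- Per deployment: 50–100 × 24 = 1,200–2,400 enrolled, which does not fit the stated total.

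**5. Tract coverage per deployment.**

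| Patients per deployment | Lower end | Upper end | Stated coverage is larger by |
|---|---|---|---|
| 200–250 (text) | 200/4,000 = 5% | 250/2,500 = 10% | – |
| 50–100 (table) | 50/4,000 = 1.25% | 100/2,500 = 4% | 2.5 to 4 times |
| 25–50 (50–100 per week) | 25/4,000 = 0.6% | 50/2,500 = 2% | 5 to 8 times |

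All of these are upper bounds. Section 3.1 places the units near the identified neighbourhood, and some attendees may live outside the tract.

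**The case against.** These are forecasts, and Section 6.1 itself says positivity will vary with the epidemiology. No power calculation, test or analysis in Section 6 uses the treated count or the tract coverage. The 600–1,200 total appears in Sections 3.1, 4.1 and 6.1 (setting aside an evident misprint of 1,200), so accrual can still be judged. All of that stands, and it limits the weight of the point.

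Three further arguments deserve an answer.

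- *The 80% may be a mislabelled factor, such as uptake among positives, so 430 may not rest on 80% positivity.* Possible, but the plan does not say so, and what is printed contradicts the 10–20% in the same paragraph.
- *With 24 deployments at 50–100 each, the treated range is 108–432, and 430 sits at its top.* True, but that needs up to 2,400 enrolled, twice the stated maximum. The ratio of 2.0 therefore holds on the 600–1,200 plan and not on every reading.
- *216 is not an established correct value.* Symptom onset within 48 hours is an inclusion criterion (Section 4.1.1), so it is unclear why 10% of enrolled positives would fall outside the window. Without the 90% factor the range is 60–240. This also stands: 54–216 is what the table's inputs give, and 180 follows from neither version.

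The conflict between 12 and 24 deployments may be a single slip, with weeks labelled as deployments. It still needs correcting.

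**Conclusion.** The point holds. There are three separate inconsistencies.

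- The table's upper end should be 216 on its own inputs; the printed 180 is 17% too low.
- The opening text of Section 6.1 does not fit the 600–1,200 plan. Its 430 treated is 2.0 times the maximum on that plan, its enrolment per deployment implies 2,400–6,000 patients, and its tract coverage is 2.5 to 8 times too high.
- The deployment count (12 against at least 24) and the unit of 50–100 (per week against per deployment) conflict.

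The sizes assume that 600–1,200 enrolled, 10–20% positivity and the 90% factor are kept. The 24 deployments assume exactly the minimum of two a week for 12 weeks. The error lies in stated planning figures and not in a power calculation. It should be fixed, because these are the only figures offered for how many patients will be treated and how far each deployment reaches into a tract.

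**What to change.** The sponsor should confirm one set of inputs (enrolment per week or per deployment, number of deployments, positivity, share in window) and derive every other figure from it.

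If 600–1,200, 10–20% and 90% are kept:

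- Change 54–180 to 54–216, and explain the 90% factor in view of the 48-hour inclusion criterion.
- Remove 430 and the 80% factor.
- Remove 200–250 enrolled and 20–50 eligible per deployment. Alternatively, replace them with 50–100 enrolled and 5–20 positive, or with 25–50 enrolled and about 2.5–10 positive if 50–100 is a weekly figure over two deployments.
- Reconcile 12 with at least 24 deployments, and use one unit for 50–100 in Sections 3.1 and 6.1.
- Restate tract coverage per deployment as at most 1.25–4%, or at most about 0.6–2%, and label it an upper bound.
- Optionally, label the 60–120 eligible as the 10% positivity case.

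If 200–250 per deployment is the intended input, the 600–1,200 total must change instead, to 2,400–3,000 (12 deployments) or 4,800–6,000 (24). At 10–20% positivity and 90% in window, expected treated becomes 216–540 or 432–1,080. The 80% would still need to be removed or given its correct meaning.

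The cost is text only, once the inputs are confirmed. If 600–1,200 is kept, the stated reach becomes less favourable.

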## **6.2 PLANNED EFFICACY EVALUATIONS**

This is an observational study of the population. Individual patient efficacy will not be assessed.

## **6.3 SECONDARY EFFICACY VARIABLES**

Census tracts and hot spot/testing desert scores are the efficacy variables.

## **6.4 SAFETY ANALYSES**

The safety analysis population will consist of all patients who received at least one dose of study drug.

## **6.5 METHOD OF ANALYSIS**

The analysis population for the efficacy analyses will consist of measuring the hot spot score in SVI-paired census tracts not receiving intervention during the study.

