Study ML44485 was therefore designed to use our Respiratory Infection Hot Spot Algorithm that identifies and supports deployment of mobile testing units to community centers, parks and senior centers in socially and economically disadvantaged communities to deploy a mobile test-to-treat model for Influenza A&B, along with testing for SARS-CoV-2 in socially vulnerable communities. This study will target communities with high rates of respiratory infection or insufficient testing for a screen and treat program for influenza. Matched communities based on the census track-based SVI will be compared to assess impact of the screen and treat program on influenza rates at a population level.

This study seeks to demonstrate that the laboratory can mitigate respiratory virus transmission in underserved populations through (1) use of analytics to identify

communities that are at risk for uncontrolled viral spread and (2) patient perception of a mobile screen and treat model for influenza.

In summary, there is a strong rationale and a positive benefit risk assessment for studying Xofluza in a screen and treat model for socially vulnerable communities and results from the Hayden et al study suggests that Xofluza has an acceptable clinical safety profile and could benefit patients who test positive for influenza. The benefit-risk ratio for Xofluza is expected to be acceptable in this setting.

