## **2. OBJECTIVES AND ENDPOINTS**

### **2.1 PRIMARY OBJECTIVE(S)**

This study seeks to demonstrate that the laboratory can mitigate respiratory virus transmission in underserved populations by using laboratory data to identify communities at risk for increase vial activity (hot spots) and intervening with a test-to-treat model provides increased access to influenza diagnostics and treatment in vulnerable and underserved communities.

1. The hot-spot frequency and hot spot score trend will be measured for each census tract to determine if the screen and treat intervention has an impact on reducing hot spot identification or hot spot score.
  - a. Following each mobile intervention, we will evaluate the hot spot score for the census tracts receiving a mobile screen and treat intervention and SVI-matched census tract not receiving an intervention for 14-days following the screen and treat intervention.
  - b. Patients will receive a follow-up phone call 14-days following their initial screening visit to assess patient and household symptoms and the socioeconomic impact of their test result and treatment access.

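### Section 6.5 defines the efficacy set as untreated census tracts only and states no contrast, so as written it cannot estimate the effect in the primary objective

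*Combined protocol and SAP*

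**What the plan says.** Section 6.5 is a single sentence: "The analysis population for the efficacy analyses will consist of measuring the hot spot score in SVI-paired census tracts not receiving intervention during the study". It names no estimator, baseline, model, test or interval, and does not say how the pairing is used.

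The objectives and rationale describe something different. Section 2.1, item 1a, says the study will "evaluate the hot spot score for the census tracts receiving a mobile screen and treat intervention and SVI-matched census tract not receiving an intervention". The evaluation is triggered "Following each mobile intervention" and runs "for 14-days following the screen and treat intervention". Item 1 of the same section adds two outcomes: "The hot-spot frequency and hot spot score trend will be measured for each census tract". Section 1.3 states: "Matched communities based on the census track-based SVI will be compared to assess impact of the screen and treat program on influenza rates".

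The rest of Section 6 does not fill the gap. Section 6.1 gives enrolment and deployment projections, 6.2 rules out individual-level efficacy, 6.3 lists tracts and scores as variables, and 6.4 defines the safety population. On frequency, 6.1 says: "The mobile testing unit will be deployed a minimum of 2 times per week". It puts the season at about 12 weeks, while its table enters 12 as the number of deployments.

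**The concern.** An intervention effect is a contrast between places that received the intervention and places that did not. A set made only of the second group can describe background influenza activity and nothing more. To answer the primary objective, the analyst must depart from 6.5 and choose the contrast, the baseline, the unit and the outcome. With none of these fixed in advance, a claim of reduced transmission could rest on an analysis chosen after the scores were seen.

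Two features of the design make those choices matter.

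- Dependence: item 1a opens a 14-day window after every visit. If a tract is revisited within 14 days, or one control tract serves several visits, the same days of data enter more than one window. The plan has no rule for this.
- Selection: Section 3.1 sends the unit to tracts because they meet the hot spot or testing desert criteria, while controls are matched on SVI alone. A tract picked when its hot spot score is high will tend to show a lower score later even if the visit does nothing.

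**Working it through.** **1. The passages side by side**

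| Place | Deployed tracts | SVI-matched undeployed tracts | Comparison stated |
|---|---|---|---|
| 1.3 | yes | yes | yes, on influenza rates |
| 2.1, item 1a | yes | yes | both evaluated, no summary measure |
| 6.5 | no | yes | no |

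Write D for the mean post-deployment score in deployed tracts and C for the same mean in their matches. Any effect measure needs both, for example D − C. The set in 6.5 supplies C only, so the effect cannot be estimated from it.

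**2. The deployment count (6.1)**

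- The table's enrolment reproduces: 12 × 50 = 600 and 12 × 100 = 1,200.
- Its count of 12 does not follow from the text: 2 per week × 12 weeks = 24, and that is a minimum. Twelve is reached only at one visit a week.
- The text gives 50–100 patients per week, and the table gives 50–100 per deployment. The 12 may therefore be a count of weeks, but the plan does not say so.

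**3. Calendar overlap of 14-day windows**

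Two windows overlap if their starts are fewer than 14 days apart. Assumed schedules: one visit every 7 days, or two visits a week at days 0 and 3.

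| Deployments | Overlapping pairs | All pairs | Most disjoint windows |
|---|---|---|---|
| 12 | 11 | 12 × 11 / 2 = 66 | 6 |
| 24 | 23 + 22 + 21 = 66 | 24 × 23 / 2 = 276 | 6 |

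At 12 visits each window overlaps only the next one. At 24 it overlaps the next three. In both cases the disjoint windows start on days 0, 14, 28, 42, 56 and 70.

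**4. Overlap at the same place**

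Calendar overlap may involve different tracts. Overlap at one place depends on the visit order, which is not given. Taking the 20 partner centers in 6.1 as the only sites (an assumption):

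- Strict rotation at 2 per week returns to a center after 20 / 2 = 10 weeks, or 70 days, so no same-center windows overlap.
- Random choice of center gives an expected 66 / 20 = 3.3 overlapping same-center pairs with 24 visits, and about a 97% chance of at least one. With 12 visits it gives 11 / 20 = 0.55 pairs and about a 43% chance.

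The plausible range therefore runs from none to several. These are counts by center; the documents do not map centers to tracts.

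**5. What cannot be computed**

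The plan gives no alpha, power, effect size, score variance, scoring frequency, within-tract correlation or matching ratio. No error in the standard error can be derived from it.

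**The case against.** The strongest reply is that the intent to compare is plain. Sections 1.3 and 2.1 name both groups, and calling the tracts in 6.5 SVI-paired implies a partner. On this view 6.5 is badly worded rather than a decision to drop the intervention tracts. That is fair as to intent. It does not rescue the analysis, because 6.5 is the only text on method, its population is wrong as written, and no other section supplies an estimator or model.

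Three stronger readings are tempting, and the documents do not support them.

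- *The plan counts overlapping windows as separate evidence.* Item 1a sets only when scores are evaluated. How windows are combined is unspecified.
- *Repeat visits are forced because 24 exceeds 20.* This needs 24 deployments where the table says 12. It also needs every visit to go to one of the 20 centers, although Sections 1.3 and 3.1 also allow parks and senior centers, and it treats centers as tracts.
- *Ignoring correlation must make standard errors too small.* The direction depends on the estimator. Suppose daily scores have variance σ² and equal correlation ρ. The variance of a 14-day mean is then σ²(1 + 13ρ)/14, larger than the naive σ²/14. The variance of a post-minus-pre change between two such means is 2σ²(1 + 13ρ)/14 − 2ρσ² = 2σ²(1 − ρ)/14, smaller than the naive 2σ²/14. Daily scoring and ρ are not in the documents.

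A reader might also see a conflict over who counts as a control: undeployed in the 14-day window (2.1) or undeployed throughout (6.5). The natural reading of 2.1 is that the 14 days describe the evaluation period. Section 6.5 then supplies the control rule, and there is no contradiction.

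**Conclusion.** The point holds in this form. Section 6.5 omits the intervention tracts that 2.1 and 1.3 include and states no contrast, so followed literally it cannot answer the primary question. This rests on the text alone and needs no assumption.

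In addition, the plan has no rule for repeat visits, overlapping windows or reused controls, and its deployment count differs by a factor of two (24 / 12). Overlap in calendar time follows from any roughly regular schedule at either count. Overlap within a tract is possible but not established. No inflation of standard errors or of false-positive risk is claimed.

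The defect should be corrected before analysis. It affects the primary objective and is cheap to repair, since about 140 tracts are already to be followed (4.1 and 6.1).

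**What to change.** Restate Section 6.5 along these lines:

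- **Efficacy set.** Every census tract with at least one deployment, plus its SVI-matched tract or tracts with no deployment at any time in the study. This keeps the control rule already in 6.5. State the matching ratio and whether a control may be reused.
- **Primary estimate.** The within-pair difference, deployed minus control, in hot spot score over the 14 days after deployment, adjusted for the pre-deployment score in both tracts. Matching controls on that score as well as on SVI is an alternative. An unadjusted change score should be avoided, because deployed tracts selected for high scores would tend to regress toward the mean in favor of the intervention. State where hot-spot frequency and score trend stand relative to this estimate.
- **Unit and interval.** Use the tract or matched set as the unit, with one summary score per tract per window. Base the interval on clustering or permutation that allows for repeat visits and for controls shared between pairs. Clustering on the pair alone does not cover a shared control.
- **Repeat visits.** Say in advance how a second visit inside an open window is handled.
- **Deployment count.** Reconcile 12 with 24 in Section 6.1.

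The cost is revised wording, somewhat more analysis work and possibly wider intervals. The scores needed come from tracts already being tracked.
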